We expect to determine substantial heterogeneity in the responses, primarily between northern and southern Europe and central and southern Europe, and generally between countries with high vs low palliative care service integration.

High palliative care score will be defined as presence of at least 16 positive responses (out of 24 possible positive responses) to question groups 10 through 14 of survey section 2.

Generalized estimating equations (GEE) models with robust SEs and exchangeable working correlation structure accounting for the factor center (24) will be applied to examine associations between a high palliative care score, the 9 clinician demographic variables of survey section 1 [with "country" stratified according to "northern, central or southern European region" (17,23,24)], and the EOL practice score and/or its subcomponent EOL practice variables listed in question group 24 of survey section 4. The dependent variable in this analysis will be high palliative care score, yes or no. Reference category for region will be "southern Europe" (17). The maximum number of GEE explanatory variables will be 21. Consequently, our target sample size of 500 participants is expected to result in approximately 24 observations (i.e. response data-points) per variable; this exceeds the recommended threshold of 20 observations per variable (17,23,24,25) by 20% and establishes an adequate safety margin, aimed at addressing the possibility of missing responses.

Significance will be set at two-sided $P < 0.05$. Analyses will be conducted using the latest versions of SSPS or R software.

Expected general benefits from the current study

Survey results will likely serve to refine the EPIC harmonized practice model of palliative care, further clarifying the concepts of primary versus specialist palliative care and ICU clinicians' role in the practice concept. Results from the survey on legal issues are expected to inform stakeholders involved in policy and legislation, and improve security for ICU clinicians in the respective countries and Europewide.

Expected benefits for the conduct of the EPIC trial

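### The safety margin claimed for 500 respondents is not established for the yes/no GEE model: it counts all respondents per questionnaire item, while the rarer-class count and the number of fitted terms are not stated

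*Combined protocol and SAP*

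**What the plan says.** The Statistical analysis plan fits a GEE model with an "exchangeable working correlation structure accounting for the factor center". On the outcome it says: "The dependent variable in this analysis will be high palliative care score, yes or no". The explanatory variables are the nine demographics of survey section 1, with country grouped into three regions, "and the EOL practice score and/or its subcomponent EOL practice variables listed in question group 24 of survey section 4". The cap is explicit: "The maximum number of GEE explanatory variables will be 21". That number equals the nine demographic questions plus the twelve items of question group 24.

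The sample size argument follows directly: "Consequently, our target sample size of 500 participants is expected to result in approximately 24 observations (i.e. response data-points) per variable". The plan then sets this ratio against a benchmark for which it cites four sources: "this exceeds the recommended threshold of 20 observations per variable (17,23,24,25) by 20% and establishes an adequate safety margin". The surplus is given a purpose, namely cover for unanswered questions ("aimed at addressing the possibility of missing responses").

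Study participants and protocol approval gives 500 as a minimum and refers to this section for its basis. No power, precision or effect-size argument appears anywhere.

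**The concern.** Two features of the model do not match the unit being counted.

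First, with a binary dependent variable, the information about coefficients is limited by the smaller outcome class, not by the total number of respondents. Reference 25, one of the four sources cited for the threshold, is by its title a simulation study of events per variable. The plan counts all respondents and gives no expected proportion with a high score.

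Second, a questionnaire item is not a model term. Several section 1 items have many categories or allow multiple answers, and each is counted once. One of the nine, hospital/city, is in substance the centre that defines the GEE clusters.

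This ratio is the only stated reason for 500, and it supports the only regression in the plan, whose associations will be judged at two-sided P < 0.05. Respondents may decline any question, and the margin is offered as cover for exactly that. A reader would take it as assurance that a 21-variable model is well supported.

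**Working it through.** **Inputs.** From the Statistical analysis plan: 500 respondents, at most 21 variables, threshold 20, binary outcome, region in three levels with a declared reference ("Reference category for region will be" southern Europe). From the Appendix: religion has 10 options (question 3); hospital/city is question 5; question 6 has three sub-items; questions 7 and 8 allow several answers; experience has four levels (question 9); the EOL practice score is the sum of its 12 binary items. The proportion scoring high is not given, so splits of 50/50, 70/30 and 80/20 are assumed as a range.

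**1. The plan's figure.** 9 + 12 = 21 and 500/21 = 23.81, about 24. Margin: 24/20 − 1 = 20% (unrounded, 23.81/20 − 1 = 19.0%). The figure is reproduced. In this unit, 20 × 21 = 420 complete cases are needed, so the margin covers a loss of (500 − 420)/500 = 16%.

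**2. Rarer outcome class.** Its size is 500 × min(p, 1 − p), which is largest at p = 0.5: 250. For 21 variables:
- 50/50: 250/21 = 11.9
- 70/30: 150/21 = 7.1
- 80/20: 100/21 = 4.8

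The 11.9 is a ceiling at 500 respondents and needs no assumption about p.

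**3. Terms instead of items, in the plan's own unit.** Twenty respondents per term holds up to 500/20 = 25 terms. With centre only as the cluster there are 8 demographics + 12 components = 20 items. Region as 2 terms makes 21. Religion as 9 terms makes 21 − 1 + 9 = 29, and 500/29 = 17.2.

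A full-category coding, again an assumption, would be age 1, gender 2, religion 9, region 2, ICU type 3, university affiliation 1, beds 1, focus 5, grade 5, experience 3 = 32. With the 12 components that is 44 terms, and 500/44 = 11.4. Using 4 terms each for focus and grade gives 42 terms and 11.9.

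**4. Both ratios on one denominator.** Centre is the cluster only, region is 2 terms, and every other item is 1 term unless noted. The component model has 9 + 12 = 21 terms and the score model 9 + 1 = 10. The 21 here is a count of terms; it coincides with the plan's 21 items because dropping hospital/city offsets the extra region term.

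| Model | k | 500/k | Rarer class per term, 50/50 | 70/30 | 80/20 |
|---|---|---|---|---|---|
| 12 components | 21 | 23.8 | 11.9 | 7.1 | 4.8 |
| Score only | 10 | 50.0 | 25.0 | 15.0 | 10.0 |
| 12 components, religion by category | 29 | 17.2 | 8.6 | 5.2 | 3.4 |
| Score only, religion by category | 18 | 27.8 | 13.9 | 8.3 | 5.6 |

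All figures assume 500 complete responses. They make no allowance for clustering within the targeted 100 or more ICUs, because no intra-centre correlation is given.

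**The case against.** The strongest reply is that the plan states its threshold per observation, not per event, and meets it: 23.8 exceeds 20 for 21 items. That stands. A reader might go further and infer that the plan fails its own threshold once rarer-class respondents are counted, or that 500 is too few. The documents do not support either inference. They set no minimum for rarer-class respondents, only the title of one of the four cited sources mentions events, and whether 20 or some other value applies on that basis cannot be checked here.

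The second reply is that the term counts are hypothetical. That is also right: only region has a stated grouping and reference, categories could be collapsed, and 21 is a maximum, so a smaller score-only model remains open. The 29 and 44 terms show how sensitive the margin is to coding that is not given; they are not a finding about what will be fitted. The score-only model stays above 20 respondents per term even with religion coded in full (27.8).

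A reader might also take the and/or wording to mean that the score and its 12 components enter together, which would be exactly collinear. The cap of 21 = 9 + 12 leaves no room for the score as a further variable, so separate models are the natural reading. They only need to be stated.

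Finally, this is a descriptive survey and 500 is a floor. Both points are true and limit the consequences, but the margin is claimed at 500 and for this model.

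**Conclusion.** The point holds as one about an unsupported assurance, and it should be fixed. The arithmetic is correct and the threshold as worded is met for 21 items. What is not established is an adequate margin for a yes/no outcome in the model that will be fitted:

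- At 500 respondents the maximal model has at most 11.9 rarer-class respondents per variable. At assumed 70/30 and 80/20 splits it has 7.1 and 4.8.
- In the plan's own unit, 20 per term is lost above 25 terms. Category coding of region and religion alone would pass that limit in the component model (29 terms, 17.2 per term). This is illustrative, because neither the coding nor the number of terms is stated.
- Hospital/city is counted as a covariate although centre is the cluster factor.

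The ratios rise in proportion if more than 500 respond. The primary and secondary outcomes are counts of yes responses and are untouched, so nothing here questions the survey's descriptive results.

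**What to change.** Change the Statistical analysis plan wording as follows.

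1. Withdraw the statement of a 20% surplus and an adequate safety margin.
2. Use centre (question 5) only as the cluster factor.
3. State that the EOL practice score and its 12 components are fitted in separate models.
4. Give the coding of each demographic and the number of fitted terms k for each model, and report both 500/k and the rarer-class count divided by k.
5. Describe the component model as exploratory.

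Suitable replacement text:

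> Centre enters only as the cluster factor. The EOL practice score and its 12 components are fitted in separate models. With region as two terms and every other item as one term, k is at least 10 for the score model and at least 21 for the component model. With 500 complete responses and assumed outcome splits of 50/50, 70/30 and 80/20, rarer-class respondents per term are at most 25.0, 15.0 and 10.0 for the score model and 11.9, 7.1 and 4.8 for the component model, and lower with fuller category coding. The component model is exploratory.

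The final k for each model should replace these lower bounds once the coding is fixed. The cost is a less favourable stated ratio. Recruitment, the questionnaire and the primary and secondary outcomes do not change.

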Internet protocol (IP) address data will be used to ensure the uniqueness of survey participants. More specifically, unlimited, repetitive access to the questionnaire will be allowed from an IP address of a client computer until survey submission. However, following submission of the filled questionnaire through an IP address, will result in discontinuation of survey accessibility through that particular IP address.

Due to the use of snowballing dissemination and sharing of invitation links, it will not be possible to calculate the survey response rate. However, survey completion rate will actually be calculated by dividing the total number of submitted questionnaires to the number of first-survey page visitors. Furthermore, questionnaire completeness rate will be calculated by dividing the number of questionnaires without any missing response to the total number of submitted questionnaires. Missing responses will correspond to questions to which participants will have indicated that they do not wish to answer (see also above). Mutually contradictory responses from participants originating from the same study center, or the same city, or the same country constitute a possibility, especially for the third and fourth section of the survey (15, 17, 22-24). For example, two or more

participants from the same center/city/country may respond differently as regards the legal bindingness of advance directives. In such cases, mutually contradictory responses will be used to estimate the extent of country-specific variation in the perception of law and/or local palliative care practice.

Study outcomes

The primary outcomes will be the absolute numbers of positive (i.e. yes) responses to question groups 10 through 14 of survey section 2, 15 through 23 of section 3, and 24 and 25 of section 4.

Secondary outcomes will include 1) the absolute numbers of positive (i.e. yes) responses to question groups 10 through 14 of section 2 in the presence vs. absence of a positive response to question 24.12 of section 4.

Statistical analysis plan

Statistical analyses will include 1) descriptive statistics; 2) assessment of distribution normality (by Kolmogorov Smirnov test); 3) assessment of European country-/region-level heterogeneity in the responses; and 4) region-level comparisons of responses (17).

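### Regional comparisons over 86 unranked primary yes-type items use an unadjusted P < 0.05, with no stated unit, test or number of contrasts

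*Combined protocol and SAP*

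**What the plan says.** **Study outcomes.** "The primary outcomes will be the absolute numbers of positive (i.e. yes) responses to question groups 10 through 14 of survey section 2", followed by groups "15 through 23 of section 3, and 24 and 25 of section 4". No group or item is singled out or ranked.

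**Statistical analysis plan.** The listed analyses end with an assessment of country- and region-level heterogeneity and with "region-level comparisons of responses (17"), where 17 is a citation to an earlier study of end-of-life practices in European ICUs. The next paragraph says where heterogeneity is expected: "primarily between northern and southern Europe and central and southern Europe". The region variable has three levels, "northern, central or southern European region". Southern Europe is the reference category, but only in the description of the GEE.

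That GEE has one dependent variable, a high palliative care score (yes or no), and it allows for centre through an exchangeable working correlation and robust standard errors. It is the only regional model specified.

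The single rule for inference is "Significance will be set at two-sided" P < 0.05. The plan has no adjustment, testing order or false-discovery control, and no statement that P-values are exploratory.

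**The concern.** One unadjusted threshold applied across many unranked primary outcomes produces some significant regional differences by chance. Here they would not look like chance, because the plan says in advance that it expects differences between the south and the other regions, and spurious ones would seem to confirm this.

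The use of the results adds to the concern. Under the expected general benefits, the palliative care findings are meant to refine the EPIC practice model, and the findings on legal issues are meant to inform those who make policy and legislation.

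A second problem compounds the first. Region is constant within an ICU, and several clinicians may answer from the same ICU. An item comparison that treats respondents as independent would exceed its nominal 5% error, and the plan names no method for item comparisons that prevents this.

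**Working it through.** **The plan's own figures.** The plan states no error rate across outcomes. Its sample-size check reproduces (500/21 = 23.8, about 24 observations per variable), but it concerns the GEE only. Its number of section 2 items, "out of 24 possible positive responses", also reproduces, which supports the count below.

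**Yes-type items, counted from the appendix**
- Groups 10 to 14: 6 + 3 + 6 + 4 + 5 = 24
- Groups 15 to 23: 8 + 6 + 7 + 6 + 6 + 5 + 5 + 4 + 2 = 49
- Group 24: 12
- Group 25: 1 (item 25.1; the rest is free text)
- Total: 24 + 49 + 12 + 1 = 86 items in 16 groups

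The 1-to-5 importance ratings are also closed questions, but they are not primary outcomes and are not counted. Item 25.1 has graded answers, so what counts as yes needs a definition. Without it there are 85 items.

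**Expected false differences if regions do not differ.** The formula is outcomes × contrasts × 0.05. The expectation does not depend on how the items correlate. The chance of at least one, 1 − 0.95^(number of tests), does assume independent tests.

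| Unit | Contrasts per outcome | Tests | Expected false | P(at least one), if independent |
|---|---|---|---|---|
| 86 items | 1 (omnibus) | 86 | 4.3 | 0.988 |
| 86 items | 2 (north-south, central-south) | 172 | 8.6 | > 0.999 |
| 86 items | 3 (all pairwise) | 258 | 12.9 | > 0.999 |
| 16 groups | 1 | 16 | 0.8 | 0.56 |
| 16 groups | 2 | 32 | 1.6 | 0.81 |
| 16 groups | 3 | 48 | 2.4 | 0.91 |

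**Skipped items.** Groups 15 to 21 hold 8 + 6 + 7 + 6 + 6 + 5 + 5 = 43 items. Seven are opening questions, so 43 − 7 = 36 are follow-ups that can be skipped, leaving 86 − 36 = 50. The printed routing at 20.1 also bypasses 21.1, so strictly 49 items are put to everyone. On those 49 the expected counts are 49 × 0.05 = 2.45, 4.9 and 7.35 for one, two and three contrasts.

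**Clustering, if the tests ignore centre.** The targets of 500 respondents and 100 ICUs give 500/100 = 5 per ICU. Both are minimum targets, so 5 is only indicative. The documents give no ICC; 0.1 to 0.3 is an assumed range. With design effect DE = 1 + (5 − 1) × ICC, the actual two-sided error is 2 × [1 − Φ(1.96/√DE)]:
- ICC 0.1: DE = 1.4, error 9.8%
- ICC 0.3: DE = 2.2, error 18.6%

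**The case against.** The strongest reply is that the plan never says regional comparisons will be made item by item. The primary outcomes are numbers of yes-responses to question groups, which can be read as 16 counts. On that reading the expected number of false differences is 0.8 to 2.4. This stands as a limit on the size of the problem. The item reading is still the more natural one. The protocol's own example of contradictory answers is a single item, on whether advance directives bind. A total over group 18 would add up legality, comfort with the law and whether feeding is included. Totals in groups 15 to 21 are also hard to compare between respondents, because of the skipping.

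Four further points have force.
- The survey is descriptive and uses a convenience sample, and no test is attached to the primary counts. But the plan does list comparisons and a significance level. If the P-values are meant only as description, one sentence would say so.
- Complete absence of regional differences is unlikely, since several items ask about national law or guidelines. The counts are therefore the largest nominal case: only items with no true difference can yield false ones.
- Follow-ups on euthanasia, especially in children, may have so few respondents that a test is infeasible or conservative.
- The regional comparisons are referred to a cited study that cannot be consulted here, so its methods neither help nor hurt the plan.

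A reader might infer that the plan commits to 172 item tests and so builds in about 9 false findings, or, multiplying by the clustered error rates, 17 to 32 (172 × 9.8% and 172 × 18.6%). The documents support neither as a forecast. Two contrasts per item are not specified, the ICCs are assumed, and whether the item tests would ignore centre is not stated.

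**Conclusion.** The concern holds in conditional form. With 86 yes-type items in 16 unranked primary groups and a single unadjusted threshold, the number of false regional differences depends on choices the plan leaves open. If regions do not differ, it is nominally about 4 to 13 at item level and about 1 to 2 at group level. Even the most favourable scheme, 16 omnibus tests, gives a 56% chance of at least one if tests are independent; correlation between items would change that probability but not the expected counts. These counts omit the country-level heterogeneity assessment, the contrast by level of service integration, and the secondary comparison by item 24.12.

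The clustering figure of about 10% to 19% per test is separate. It rests on 5 respondents per ICU, an assumed ICC of 0.1 to 0.3, and tests that ignore centre.

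This is more than missing detail, because chance findings would match the direction announced in advance. It does not affect the descriptive counts or the GEE for the high palliative care score. It should be settled before the regional results are analysed.

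**What to change.** Amend the statistical analysis plan as follows.

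1. State the unit of regional comparison (item, group count or score), the test, and the contrasts (for example, north-south and central-south only). Define a yes for item 25.1.
2. Report item-level regional results as proportions and differences with centre-clustered 95% confidence intervals, for example from the GEE with robust standard errors already planned for the score. Show the number who answered each item, and give counts only where there are too few for a model.
3. Either control the false discovery rate across all item-by-contrast tests (for example, Benjamini-Hochberg at 5%) or state that item-level P-values are descriptive and carry no claim of significance.
4. Keep the unadjusted two-sided P < 0.05 for one or two named comparisons, such as region in the existing GEE for the high palliative care score.

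The cost is some wording and slightly more programming, with no change to the questionnaire or data collection. The downside is that fewer single items will be labelled significant.

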APPENDIX. THE STUDY QUESTIONNAIRE

Palliative care and legal aspects of treatment limitation decisions in ICU A survey of clinicians' perceptions

The primary objective of the current survey study is to obtain detailed information about European ICU clinicians' awareness of palliative care and relevant, local end-of-life (EoL) legislation.

Please note that by completing the following survey, you consent to participate in the study.

Definitions

Advance directive is an instrument that relays information concerning an individual's preferences and goals regarding medical procedures and treatments, especially those used for end-of-life care.

Advance care planning: A process that enables individuals to

- define goals and preferences for future medical treatment and care,
- thoroughly discuss these goals and preferences with family and health-care professionals
- record and review these preferences if appropriate.

The main objective of advance care planning is to help ensure that people receive medical care that is consistent with their values, goals and preferences during serious, chronic and/or acute/life-threatening illness.

Shared decision-making: shared decision-making is a collaborative process that allows patients, or their surrogates, and a possibly/preferably multidisciplinary team of healthcare professionals to reach consensus on which treatment strategies and interventions - including life-support limitation and palliative care- accord with the patient's values, goals, and preferences. [Adopted from Resuscitation. 2021;161:408-432].

Palliative care: is an approach that improves the quality of life of patients (adults and children) and their families who are facing problems associated with life-threatening illness. It prevents and relieves suffering through the early identification, correct assessment and treatment of pain and other problems, whether physical, psychosocial or spiritual (adopted from the WHO 2014 definition).

Treatment limitation/euthanasia: Treatment limitation in the form of withholding or withdrawing life-prolonging treatments should NOT be confused with euthanasia, which means active, intentional, and painless termination of a person's life by another person

acting at the request of the dying person.

Family: is defined by the patient or, in the case of minors or those without decision-making capacity, by their surrogates. In this context, the family may be related or unrelated to the patient. They are individuals who provide support and with whom the patient has a significant relationship.

Clinician Demographics

1. Age

(number)

2. Gender

Male, Female, Other

3. Religion

Buddhist, Catholic, Christian, Greek Orthodox, Hindu, Jewish, Muslim, Protestant, Other, None

4. Country of your professional activity

Austria, Belgium, Bosnia and Herzegovina, Bulgaria, Croatia, Cyprus, Czech Republic, Denmark, Finland, France, Georgia, Germany, Greece, Hungary, Iceland, Ireland, Israel, Italy, Kosovo, Montenegro, Netherlands, Norway, Poland, Portugal, Romania, Serbia, Slovakia, Slovenia, Spain, Sweden, Switzerland, United Kingdom, Other (please specify)

5. Name of hospital/healthcare facility and city of your professional activity

(free text)

6. Characteristics of your intensive care unit (ICU)

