A set of 20 consecutive random numbers (range, 10-29) will be generated using "Research Randomizer (www.randomizer.org). Each one of the aforementioned numbers will be assigned to a European country (country code) drawn according to alphabetic order from the list of participating countries. Next to the 2 digits of the country code, a one-to-three-digit number will be placed to represent each participant's temporal order of participation relative to other participants from the same country. The country-specific, temporal order of participants will be determined according to the exact time of submission of the completed study questionnaire. This will form the personal, three-to-five digit code for each study participant.

The survey database will be hosted by the CHARITE Berlin Simulation and Training Centre. Data on questionnaire domains will be stored next to the participant's personal code in Microsoft Excel format. This electronic Masterfile will be stored onto the password-protected hard disk of a personal computer. In addition, next to the participant's personal code, we will enter the following personal data 1) age; 2) gender; 3) religion; 4 and 5) country and center/city of professional activity; 6) characteristics of the participant's ICU (e.g. general, medical, surgical, etc.); 7) the participant's professional focus (e.g. clinical, research, etc.); and 8 and 9) the participant's professional grade (e.g. consultant, professor, etc.) and ICU experience (in years of work). There will be no collection/recording of participants' names or electronic mail addresses. Therefore, the Masterfile will fulfill the criterion of "*pseudonymization*."

Development and testing of the questionnaire

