6.1 General/mixed, Medical, Surgical, Other

6.2 University-affiliated, Not University-affiliated

6.3 Number of ICU beds (number)

7. Your professional focus (please choose all that apply)

Clinical, Education, Research, Management, Other (please specify)

8. Your grade (please choose all that apply)

Nurse, Trainee / non-specialist, Consultant / specialist,

University-related (Lecturer/Professor), Other (please specify)

9. Your professional intensive care experience

Less than 5 years, 5 to less than 10 years, 10 to 20 years, More than 20 years

Perceptions about provision of care for end of life / treatment limitation decisions

Please use the following 5-point scale to rate the level of importance (regarding routine/usual/standard practice) of the following domains of end-of-life patient care. Please note that the term "importance" corresponds to what the clinician considers as important for the care of ICU patients who are nearing end-of-life and have a documented poor prognosis.

1=unimportant
 2=low importance
 3=average importance
 4=high importance
 5=maximum importance

At the end of each domain, it is possible to clarify your responses and/or add other comments

10. Physical aspects of care

10.1. The patient's pain is assessed at least once daily, depending on their individual needs

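### Question 3 lists Christian beside three Christian denominations with no precedence rule, so religion cannot be classified consistently by denomination for the GEE

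*Combined protocol and SAP*

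**What the plan says.** Question 3, under Clinician Demographics in the appendix, gives ten options: "Buddhist, Catholic, Christian, Greek Orthodox, Hindu, Jewish, Muslim, Protestant, Other, None". It does not invite more than one answer. Question 7 does ("Your professional focus (please choose all that apply"), and so does question 8, so question 3 reads as single choice. *Other* in questions 4, 7 and 8 asks the respondent to specify; *Other* in question 3 does not, and the demographic section shows no comment field.

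Religion is stored with each participant's code (Informed consent and data protection: "1) age; 2) gender; 3) religion; 4 and 5) country and center/city of professional activity"). In the Statistical analysis plan it enters the GEE as one of "the 9 clinician demographic variables of survey section 1". On the outcome of that model the plan says "The dependent variable in this analysis will be high palliative care score, yes or no". Only country has a grouping rule ("with 'country' stratified according to 'northern, central or southern European region"), and only region has a reference level ("Reference category for region will be 'southern Europe"). On model size it says "The maximum number of GEE explanatory variables will be 21".

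**The concern.** A Catholic, Greek Orthodox or Protestant respondent has two true answers and, as the item reads, may give one. An Orthodox respondent of another church has no denominational option and is left with *Christian*, *Other* or declining to answer. The country list in question 4 includes Bulgaria, Georgia, Romania and Serbia, where such respondents can be expected; that expectation is general knowledge, not a statement in the documents.

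Once a questionnaire is submitted, nothing collected allows a *Christian* answer to be reassigned to a denomination. With no coding rule in the plan, the analyst would have to choose the levels of religion with the data in hand. At stake is whether a religion coefficient from the GEE can be read at all.

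**Working it through.** **1. The plan's own figure.** 9 demographic variables + 12 end-of-life practice variables = 21. 500/21 = 23.8, which the plan rounds to 24. 24/20 − 1 = 20% above its threshold (19% unrounded). The figure reproduces. It counts religion as one variable, so the overlap does not touch it.

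**2. The overlap.** Four of the ten options are Christian: Catholic, Christian, Greek Orthodox and Protestant. The second contains the other three. No passage in the protocol, the SAP or the appendix ranks them, merges them or names a reference level.

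**3. What the overlap does to each level.** Let a share *m* of each named denomination tick *Christian*, and take every tick of a named denomination as accurate.

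- *Named denominations.* If the high-score rate is *p* in a denomination and *q* among those of its members who tick *Christian*, the rate among those who remain is (*p* − *mq*)/(1 − *m*). For *m* > 0 this equals *p* only when *q* = *p*. So the expected contrast between named denominations is unchanged unless ticking *Christian* is related to the outcome. With equal *m*, standard errors grow by about 1/√(1 − *m*).
- *The Christian level.* It combines those with no better option and those displaced from the three denominations, in proportions that nobody can recover.

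**4. Illustration.** Every input except 500 is assumed; the documents give no shares or rates. Shares: Catholic 35%, Protestant 20%, Greek Orthodox 20%, Christian of no listed denomination 5%. High-score rates: 50%, 65%, 40% and 70%. Ticking is taken as unrelated to the outcome within a denomination.

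Size of the *Christian* level = 0.05 + 0.75*m*. Its rate = (0.05 × 0.70 + *m* × (0.35 × 0.50 + 0.20 × 0.65 + 0.20 × 0.40))/(0.05 + 0.75*m*) = (0.035 + 0.385*m*)/(0.05 + 0.75*m*).

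| *m* | Catholic level, of 500 | Christian level, of 500 | Part of Christian level from a named denomination | Rate in Christian level | OR Christian v Catholic | OR Protestant v Catholic | SE factor, named contrasts |
|---|---|---|---|---|---|---|---|
| 0% | 175 | 25 | 0% | 70.0% | 2.33 | 1.86 | 1.00 |
| 10% | 157.5 | 62.5 | 60% | 58.8% | 1.43 | 1.86 | 1.05 |
| 20% | 140 | 100 | 75% | 56.0% | 1.27 | 1.86 | 1.12 |
| 30% | 122.5 | 137.5 | 82% | 54.7% | 1.21 | 1.86 | 1.20 |

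The *Christian* coefficient moves a long way. The Protestant v Catholic contrast stays at (0.65/0.35)/(0.50/0.50) = 1.86 and loses precision only.

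**5. Merging.** With the four options combined, the level holds 80% of respondents and has a rate of 0.42/0.80 = 52.5% at every *m*. The overlap then has no effect.

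**6. Terms in the model (a side check).** If religion enters as indicators and the other 20 variables count once each, as the plan counts them, ten levels give 9 terms: 500/(20 + 9) = 17.2 observations per term. Relabelling keeps ten levels and 17.2. Merging gives seven levels and 6 terms: 500/26 = 19.2. This follows from coding and not from the overlap, but it is another reason to state the levels.

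**The case against.** The strongest reply is that a Catholic who sees *Catholic* will probably choose it, leaving *Christian* to work as a residual category. The documents cannot show how often that fails. The questionnaire was also pretested for clarity in 30 clinicians. The first part stands as a limit on what can be claimed: the item does not allow consistent classification, but it is not shown that any given respondent will be misclassified. The pretest gives little reassurance. It covered three countries, only the 10 Greek clinicians were asked to answer the questions, and no result for this item is reported (Development and testing of the questionnaire).

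A second reply is that the plan never says the ten options will be separate levels, and merging removes the overlap. That is correct, but no merging rule is written.

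A reader might infer more than the documents support:

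- *Contrasts between denominations are diluted.* Step 3 of the working shows that they mainly lose precision. Bias needs a link between ticking *Christian* and the outcome, and nothing in the documents establishes one.
- *Religion becomes entangled with region.* This would need use of *Christian* to differ by country. That is plausible but undocumented, and region is itself in the model.
- *The item exists to measure denomination.* The protocol only lists religion among participant characteristics.
- *A stated number of respondents is lost.* Any headcount multiplies two assumptions, a denomination's share and a ticking rate.

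**Conclusion.** The point holds as a flaw in one response set. Used as listed, question 3 yields a *Christian* level of unknown composition with an uninterpretable coefficient, and named denominations that are smaller than they should be. Bias between named denominations is conditional on ticking *Christian* being related to the outcome.

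The conclusion rests on reading question 3 as single choice, on religion being entered with the options as printed, and on ticks of a named denomination being accurate. Its size cannot be derived from the documents; the table shows a mechanism and does not estimate anything.

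The weight is small. Religion is one of up to 21 explanatory variables in an association analysis. The primary outcomes (counts of positive responses), the secondary outcome (section 2 responses by the answer to question 24.12) and the observations-per-variable figure do not depend on it.

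**What to change.** **Before launch.** In question 3, change *Christian* to *Other Christian denomination* and *Greek Orthodox* to *Orthodox*. Add a sentence to the Statistical analysis plan giving the levels of religion in the GEE and the reference category. The cost is two edited labels and one sentence.

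**If collection has already begun** (the protocol sets it for January 1 to July 30, 2024), leave the labels alone, since a change would split the data between two versions of the item. State in the SAP, before the analysis, that the four Christian options form one GEE level, name the reference category, and make no denominational claims. The downside is loss of denominational detail. Merging also does not recover Orthodox respondents who chose *Other*, because that option has no free-text field.
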